5.3.1. Primary Efficacy Endpoint

For the primary efficacy endpoint, VOCs that meet the protocol-specified definition as assessed by the VOC Adjudication Committee with an onset date from randomization (Day 1) through the 90-day study period (Day 91), inclusive, will be used in the analysis.

The proportion of participants with at least 1 VOC that required admission to a healthcare facility and treatment with parenteral pain medication within 90 days (primary endpoint) from randomization will be compared between treatment groups using the exact Cochran-Mantel-Haenszel (CMH) general association test, stratified by the randomization stratification factors (baseline HU use [yes; no] and number of VOCs in the 12 months prior to study entry [2 to 4 episodes; 5 to 10 episodes]).

Every effort will be made to obtain the 90-day re-admission status for a VOC for each participant. For purposes of the primary analysis, participants with an unknown 90-day readmission status (e.g., participants who discontinue the study prior to 90 days and without a readmission for a VOC) will be classified as having experienced at least 1 protocol-defined VOC within 90 days (i.e., counted as "failure"). A sensitivity analyses based on observed data (i.e., without imputation of re-admission for early study discontinuation) will be performed to assess the robustness of the primary analysis results to assumptions regarding drop-outs.

SAS code for the exact CMH test similar to the following will be used for the primary analysis (where trtgrp is the randomized treatment group and response is an indicator variable for occurrence of at least one protocol-defined VOCs during the 90 days post randomization):

```
PROC LOGISTIC;
CLASS trtgrp /PARAM=REF;
MODEL response (event='Yes') = trtgrp;
STRATA = <categorical variables>;
EXACT trtgrp;
RUN;
```

Similarly, the proportion for each treatment group and the difference in proportions between treatment groups (inclacumab versus placebo) will be estimated by the weighted average of the observed proportions and the differences in observed proportions over the strata using the CMH weights and 95% confidence intervals (CIs) provided (Mehrotra and Railkar 2000).

5.3.2. Secondary Efficacy Endpoints

5.3.2.1. Time to First VOC

Time to first VOC that required admission to a healthcare facility and treatment with parenteral pain medication within 90 days will be measured from randomization (Day 1) to onset date of the first protocol-defined VOC event. For participants who do not experience a protocol-defined VOC within 90 days of randomization, time to first VOC will be censored at the end of their time at risk (participant's end of study date or Study Day 91, whichever is earlier).

Summary statistics will include number of subjects with event, number of subjects censored, median time to event along with 95% CI for the median and quartiles. The CIs for the median will be calculated according to Brookmeyer and Crowley (1982) and the CIs for the survival function estimates at fixed time points will be derived using the log-log transformation according to Kalbfleisch and Prentice (2002) (conftype=loglog default option in SAS Proc LIFETEST) with back transformation to a CI on the untransformed scale. The estimate of the standard error will be computed using Greenwood's formula.

Treatment comparison between inclacumab and placebo will be performed based on log-rank test stratified by the randomization factors of baseline HU use and number of VOCs in the 12 months prior to study entry. Kaplan-Meier plots will be generated. A Cox regression model will be used to estimate the hazard ratio between the inclacumab and placebo groups, as appropriate.

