3.3.3.1. Early Discontinuation of Individual Participants

Participants will be informed that they are free to withdraw from the study at any time and for any reason. The Investigator must withdraw from the study any participant who requests to be withdrawn. Participants who ask to leave the study early (withdraw consent) should be encouraged to undergo the tests and evaluations listed for the Early Termination (ET) Visit (ie, early termination is intended for participants who withdraw consent). If a participant

withdraws before completing the study, the date and reason for withdrawal is to be documented on the electronic case report form (eCRF).

Participants may discontinue the study for any of the following reasons:

- Adverse event
- Withdrawal of consent
- Discretion of the Investigator
- Participant is lost to follow-up
- Participant is noncompliant
- Pregnancy. Report the pregnancy according to the instructions in Section 7.4.

A participant that withdraws from the study or is lost to follow-up will not be replaced.

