8.4.3.2. Secondary Endpoints

For time to first VOC that required admission to a healthcare facility and treatment with parenteral pain medication within 90 days, treatment comparison will be performed based on a log-rank test stratified by the randomization factors and Kaplan-Meier plots generated. For participants who do not experience a VOC that required admission to a healthcare facility and treatment with parenteral pain medication within 90 days of randomization, time to first VOC will be censored at the end of their time at risk (date of last study assessment or Study Day 91, whichever is earlier).

For the proportion of participants with at least 1 VOC that required admission to a healthcare facility and treatment with parenteral pain medication within 30 days, the same statistical methods used for the primary efficacy endpoint will be used.

For the rate of VOCs leading to a healthcare visit within 90 days, the total number of VOCs in the 90-day period will be compared between treatment arms using a negative binomial regression model stratified by the randomization factors.

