2. INTRODUCTION

The primary objective of Study GBT2104-132 (C5361002) is to evaluate the safety and efficacy of a single dose of inclacumab compared with placebo to reduce the incidence of re-admission to a healthcare facility for a vaso-occlusive crisis (VOCs) after an admission for an index VOC in participants with sickle cell disease (SCD). However, as of June 2023, the Sponsor decided to discontinue Study GBT2104-132 early, prior to full enrollment. The decision is based on business considerations and not due to any specific safety reason or request from any regulatory authority.

This statistical analysis plan (SAP) provides details of the planned analyses and statistical methods for Study GBT2104-132. In many instances, analyses have been limited and/or are descriptive in nature, due to the early discontinuation of the study.

Where this document differs from the high-level analysis plan described in the study protocol, the methodology described in this SAP is considered the latest and supersedes the corresponding section(s) in the protocol.

Population pharmacokinetic (PK), exploratory pharmacodynamic (PD), and exploratory biomarker analyses will be described in a separate document.

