3. GENERAL CONSIDERATIONS

3.1. Definitions and Terminology

Study Drug

The term study drug refers to either inclacumab or placebo.

Baseline Value

Baseline is defined as the last available pre-treatment value taken on or before the day of randomization, and will be used for summary of baseline characteristics and change-from-baseline analyses, as appropriate. For ASCQ-Me, baseline is defined as the assessment taken on the day of randomization.

Day 1

Day 1 is the date of randomization.

Study Day

Study Day is defined relative to the date of randomization.

For study assessments or events that occur on or after the date of randomization, study day is calculated as:

Study Day = Event Date - Randomization Date + 1.

For study assessments or events that occur before the date of randomization, study day is calculated as:

Study Day = Event Date – Randomization Date.

Study Visit

Study Visit is the protocol visit as shown in Table 1.

Treatment Day

Treatment Day is defined relative to the date of first dose of study drug.

For study assessments or events that occur on or after the date of first dose, treatment day is calculated as:

Treatment Day = Event Date - First Dose Date + 1.

For study assessments or events that occur before the date of first dose, treatment day is calculated as:

Treatment Day = Event Date – First Dose Date.

Treatment-Emergent Adverse Event

Treatment-emergent adverse events (TEAEs) are defined as adverse events that occur on or after Day 1 of study treatment or the worsening of a preexisting condition on or after Day 1 of study treatment. Note: Given the long half-life of inclacumab, events occurring through end of study will be considered treatment emergent.

Study Completion

Completion of study is specified on the End of Study (EOS) CRF. Participants are considered to have completed the study if (1) the subject completed the study through the Day 91 visit and elected to enroll in the open-label extension study, or (2) the subject did not enroll in the open-label extension study and completed the study through the Day 161 visit.

Treatment Completion

Completion of treatment is specified on the End of Treatment (EOT) CRF and includes all participants who did not permanently discontinue study drug early.

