5.2. Summaries of Demographic, Baseline Characteristics, and Concomitant Medications

Demographic and baseline characteristics (such as age, sex, race, body weight in kg, estimated glomerular filtration rate [eGFR], sickle cell genotype, number of VOCs in the 12 months prior to the screening visit, baseline HU use, baseline voxelotor use, prior crizanlizumab use, and geographic region) will be summarized for the ITT population by treatment group.

Medical history will be coded using Medical Dictionary for Regulatory Activities (MedDRA; the most current version at the time of the analysis will be used) and summarized for each treatment group. Prior and concomitant medications will be coded using the World Health Organization (WHO) Drug Dictionary and summarized.

Time on study, defined as time from randomization (Day 1) to the participant's end of study date, will also be tabulated.

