5.3.2.3. Rate of VOCs Leading to Healthcare Visit and Requiring Parenteral Pain Medication

For the rate of VOCs leading to a healthcare visit within 90 days, the total number of VOCs in the 90-day period will be compared between the treatment groups using a negative binomial regression model stratified by the randomization factors of baseline HU use and number of VOCs in the 12 months prior to study entry. For each participant, the time period at risk for evaluation of VOCs is from date of randomization (Day 1) to the participant's end of study date or Study Day 91, whichever is earlier.

The regression model will include covariates for treatment group (inclacumab, placebo) and the randomization stratification factors. The logarithm of observed patient-time at risk will be used as an offset term in the model to account for different lengths of follow-up across participants. The rate of VOCs adjusted for the specified baseline covariates will be estimated for each treatment arm based on the regression model. Similarly, the ratio of the VOC rate (inclacumab versus placebo) along with the associated 95% confidence interval (CI) and p-value will be estimated from the regression model.

A plot of the mean cumulative function of VOC episodes will be presented using recurrent events analysis methods.

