5.3.3. Exploratory Efficacy Endpoints

Exploratory endpoints will be summarized by descriptive statistics. For comparison between inclacumab and placebo groups, point estimates, CIs, and p-values may be presented as appropriate, without adjustment for multiplicity.

Time to second VOC that required admission to a healthcare facility and treatment with parenteral pain medication within 90 days will be measured from randomization (Day 1) to onset date of the second protocol-defined VOC event and summarized using the same methodology as for time to first VOC (secondary endpoint).

The rate of complicated VOCs, rate of inpatient hospital admissions, and number of days of inpatient hospitalization for any reason during the 90 days following randomization will be summarized descriptively, using similar patient-time methodology as the rate of VOCs leading to a healthcare visit (secondary endpoint).

The proportion of participants rated as "very much improved" or "much improved" based on the PGI-C at Day 46 and Day 91 will be summarized descriptively by timepoint and treatment group. A similar analysis will be performed for the proportion of participants rated as "very much improved" or "much improved" based on the CGI-C.

A cumulative score for the ASCQ-Me Pain Impact (Short Form) will be calculated for each participant and assessment timepoint. For each assessment a cumulative score will only be calculated if all five questions on the form were answered. The cumulative score is the sum of the individual raw scores according to the response mapping in Table 3.

Table 3: ASCQ-Me Pain Impact (Short Form) Response Mapping

Response to Each Question	Raw Score
Always	1
Often	2
Sometimes	3
Rarely	4
Never	5

Changes from baseline over time to Day 91 will be calculated and summarized descriptively by timepoint (weekly) and treatment group.

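### Does the SAP's end of study date count unobserved days as event-free for participants lost to follow-up?

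*SAP*

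**What the plan says.** Protocol 8.4.3.2 censors a participant without a qualifying VOC at the "date of last study assessment or Study Day 91, whichever is earlier". SAP 5.3.2.1 uses instead the participant's "end of study date or Study Day 91, whichever is earlier". The SAP states that where the two documents differ "the methodology described in this SAP is considered the latest and supersedes the corresponding section(s) in the protocol", so the SAP date governs.

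SAP 5.3.2.3 ends the risk period for the VOC rate at the same date. There it replaces nothing, because the protocol gave no risk period for that endpoint. It adds: "The logarithm of observed patient-time at risk will be used as an offset term in the model". SAP 5.3.3 carries both methods into the exploratory analyses of second VOCs, complicated VOCs and inpatient stays.

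The date has no definition of its own. SAP 3.1 says "Completion of study is specified on the End of Study (EOS) CRF" and describes who counts as a completer. SAP 5.2 uses the date again: "Time on study, defined as time from randomization (Day 1) to the participant's end of study date". For a participant who withdraws, Protocol 3.3.3.1 requires that "the date and reason for withdrawal is to be documented on the electronic case report form (eCRF"). For a participant who is lost, Protocol 3.3.4 gives a process (a missed visit, at least two calls, a certified letter) but assigns no date.

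**The concern.** The protocol's date was tied to an assessment, that is, to a moment when VOC status could be learned. The SAP's date is tied to study exit. For completers and withdrawals the two are close or documented. For a lost participant, exit can be declared only after the contact attempts have failed, so it falls some time after the last real contact.

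If that later date is what the form holds, the days in between enter the Kaplan-Meier risk set and the negative binomial offset as time without events. Absolute rates would then be too low in both arms. If losses differ by arm, the hazard ratio and rate ratio would shift in favour of the arm with more losses. It would also sit oddly beside the primary analysis (SAP 5.3.1), which counts unknown 90-day status as a failure: someone declared lost after Day 91 would be a failure there and event-free to Day 91 here.

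**Working it through.** The plan gives no figure for this effect. Its design inputs do hold together: with 140 × 0.95 = 133 per arm, 35% against 17.5% and two-sided 0.05, power is 0.905 for a fixed design and 0.900 at the final Lan-DeMets level, against about 90% stated. That figure does not depend on the censoring rule, but the same inputs serve below.

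**Inputs from the documents.** About 26% of 280 randomized (SAP 2.3): 0.26 × 280 ≈ 73, or 36.5 per arm. Drop-out 5% (Protocol 8.2): 0.05 × 73 = 3.65, taken as 4. Risk time runs to Study Day 91.

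**Assumptions.** The recorded date is the day loss is declared; every drop-out is a loss; all have the same gap g between last contact and that date. Plausible gaps follow from the visit schedule: 15 days (Day 31 call to Day 46 visit), 22 days (to the end of the Day 46 window, Day 53) and 30 days (Day 61 call to Day 91). For simplicity each participant's recorded time is set at 91 days.

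**Step 1, added person-time.** 91/(91 − 0.05g) − 1 gives 0.8%, 1.2% and 1.7% for g = 15, 22 and 30. Absolute rates are understated by about that share, even with balanced losses.

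**Step 2, effect on the rate ratio.** With a losses on inclacumab and b on placebo, the reported ratio equals the correct one times (36.5 × 91 − a·g)/(36.5 × 91 − b·g), where 36.5 × 91 = 3321.5.

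| Losses, inclacumab:placebo | g = 15 | g = 22 | g = 30 |
|---|---|---|---|
| 2:2 | 1.000 | 1.000 | 1.000 |
| 3:1 | 0.991 | 0.987 | 0.982 |
| 4:0 | 0.982 | 0.974 | 0.964 |

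For example, 4:0 at 30 days is (3321.5 − 120)/3321.5 = 0.964. Losses weighted toward placebo give the reciprocals. If loss is unrelated to arm, all four fall on inclacumab with probability 0.5⁴ = 6%.

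**Step 3, cross-checks.** Stopping the clock at the first event (constant hazards; mean time at risk 73.8 days on placebo and 82.7 on inclacumab) gives, for 4:0 at 30 days, (36.5 × 82.7 − 120)/(36.5 × 82.7) = 0.960. A simulation with a 30-day gap and 5% lost in each arm leaves the hazard ratio at 0.448; with 10% lost on inclacumab only it moves from 0.448 to 0.432, and with 10% lost on placebo only from 0.447 to 0.464.

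**Step 4, scale against precision.** Expected first events are 36.5 × 0.35 = 12.8 and 36.5 × 0.175 = 6.4. The standard error of the log hazard ratio is √(1/12.8 + 1/6.4) = 0.48. The worst case in step 3 is |ln 0.960|/0.48 = 0.08 standard errors. For the VOC rate in SAP 5.3.2.3 the documents give no expected count, so its standard error cannot be derived; if it were half as large (0.24, assumed), |ln 0.964|/0.24 = 0.15.

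**The case for a change.** The strongest case for a change is that the wording really did move, without a stated reason, from a date tied to assessment to one that is not; that the date is left open for exactly the participants for whom it matters; and that one sentence would close it. Balanced losses protect the ratio but not the absolute rates or the Kaplan-Meier curves. Protocol 3.3.4 also sets no deadline for declaring loss, so longer gaps are possible. All of this is correct on the text.

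It carries little weight for four reasons.

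- The harm depends on the completion rules of a form that is not among the documents. If the form takes last contact for lost participants, nothing is wrong.
- The SAP states its intention. SAP 5.3.2.1 presents the censoring date as the point where risk time stops, and SAP 5.3.2.3 calls the offset observed time. Counting unobserved days means reading the date against those words. It also matches the VOC collection window in Protocol 7.6.1, which closes when a participant leaves the study.
- The protocol's date is no sharper: it does not say whether a telephone call or a weekly record is an assessment.
- The obvious remedy, ending risk time at the last site contact, has a bias of its own. Protocol 5.1 asks participants to report a VOC visit elsewhere within 48 hours. If such a report counts as a contact, it lengthens follow-up only for people with events and pushes rates up.

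Long gaps require a site to leave a missed Day 46 visit unresolved for weeks, although that visit is what starts the contact attempts. Taking every drop-out as lost is itself an upper case, since Protocol 3.3.3.1 lists several other reasons for leaving.

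**Conclusion.** This is missing detail that analysts can fill sensibly, and no change to the plan follows. The textual point holds: the SAP's date differs from the protocol's and has no rule for lost participants. Whether any bias results cannot be settled from the documents.

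If it does, then with 4 losses among about 73 participants and gaps of 15 to 30 days, absolute rates fall by roughly 1% to 2%. The rate ratio is unchanged for an even split and multiplied by no less than 0.964 when all four losses are on inclacumab; the first-event version reaches 0.960, or 0.08 standard errors. These sizes rest on assumed gaps and splits; the documents supply only the 5% drop-out and the number randomized.

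The consequences are limited too. The primary endpoint and the 30-day proportion do not use this date. The trial was stopped early for business reasons, and the SAP makes no multiplicity adjustment, so no confirmatory claim turns on the secondary or exploratory results affected.

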5.3.2.2. Participant Status with at Least 1 VOC Requiring Re-Admission with 30 Days

For the proportion of participants with at least 1 VOC that required admission to a healthcare facility and treatment with parenteral pain medication within 30 days, the same statistical methods used for the primary efficacy endpoint will be used.

5.3.2.3. Rate of VOCs Leading to Healthcare Visit and Requiring Parenteral Pain Medication

For the rate of VOCs leading to a healthcare visit within 90 days, the total number of VOCs in the 90-day period will be compared between the treatment groups using a negative binomial regression model stratified by the randomization factors of baseline HU use and number of VOCs in the 12 months prior to study entry. For each participant, the time period at risk for evaluation of VOCs is from date of randomization (Day 1) to the participant's end of study date or Study Day 91, whichever is earlier.

The regression model will include covariates for treatment group (inclacumab, placebo) and the randomization stratification factors. The logarithm of observed patient-time at risk will be used as an offset term in the model to account for different lengths of follow-up across participants. The rate of VOCs adjusted for the specified baseline covariates will be estimated for each treatment arm based on the regression model. Similarly, the ratio of the VOC rate (inclacumab versus placebo) along with the associated 95% confidence interval (CI) and p-value will be estimated from the regression model.

A plot of the mean cumulative function of VOC episodes will be presented using recurrent events analysis methods.

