3.3.1.1. Inclusion Criteria

- Participant has an index VOC. The index VOC is any VOC that required admission to a healthcare facility and treatment with parenteral pain medication. An admission for the index VOC includes:
 - a. A hospital admission, or
 - An admission to an emergency room, observation unit, or infusion center for ≥ 12 hours, or
 - 2 visits to an emergency room, observation unit, or infusion center over a 72-hour period.

for an acute episode of pain with no other cause other than a vaso-occlusive event that includes the following:

- Uncomplicated VOC,
- Acute chest syndrome (ACS),
- Acute hepatic sequestration,
- Acute splenic sequestration, or
- Priapism.
- 2. Participant has a confirmed diagnosis of SCD (any genotype).

Documentation of SCD genotype is required and may be based on documented history of laboratory testing or confirmed by laboratory testing at Baseline.

- Participant is male or female, ≥ 12 years of age at the time of informed consent.
 - NOTE: Initial study enrollment will include only participants ≥ 16 years of age until the DMC recommends to the Sponsor that adequate safety and PK data support the enrollment of participants 12 to 15 years of age. Sites will be informed by the Sponsor when participants 12 to 15 years of age may be enrolled.
- 4. Participant is able to complete screening and receive study drug within 5 days following investigator-assessed resolution of index VOC (for example, hospital discharge, discontinuation of parenteral pain medication, or transition to oral pain medication).
- 5. Participant has experienced between 2 and 10 VOCs (inclusive) within the 12 months prior to Screening as determined by documented medical history. The index VOC is not to be considered as one of the 2 to 10 events. A prior VOC is defined as an acute episode of pain that:
 - Has no medically determined cause other than a vaso-occlusive event, and
 - Results in a visit to a medical facility (hospital, emergency department, urgent care center, outpatient clinic, or infusion center) or results in a remote contact with a healthcare provider; and
 - Requires parenteral narcotic agents, parenteral nonsteroidal anti-inflammatory drugs (NSAIDs), or an increase in treatment with oral narcotics.
- Participants receiving erythropoiesis-stimulating agents (ESA, eg, erythropoietin [EPO])
 must be on a stable dose for at least 90 days prior to Screening and expected to continue

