2.3. Determination of Sample Size

The original sample size determination was based on statistical power considerations for the primary efficacy endpoint, the proportion of participants with at least 1 VOC that required admission to a healthcare facility and treatment with parenteral pain medication within 90 days of randomization.

As originally planned, the study was to use a group sequential design to evaluate the primary efficacy endpoint based on 2 sequential analyses: (i) one interim analysis after approximately 75 participants per arm have completed the study through 90 days, and (ii) if required, a final study analysis based on approximately 140 participants per arm.

For the primary endpoint, the planned sample size of up to 280 participants (140 participants per treatment group) was to provide approximately 90% power to detect a targeted 50% relative reduction in the proportion of participants with at least 1 VOC that required admission to a healthcare facility and treatment with parenteral pain control within 90 days, from a rate of 35% for placebo to 17.5% for inclacumab, using a 2-sided test of the difference in 2 binomial proportions (Normal approximation). To maintain an overall Type I error rate of 0.05, calculations assumed an O'Brien-Fleming boundary of the Lan-DeMets alpha-spending function (East® version 6.5). For the sample size calculation, a 5% drop-out rate during the 90-day study period was used.

With this original sample size, the smallest observed treatment difference expected to be statistically significant at the final analysis was approximately a 32% relative reduction (i.e., reduction in the proportion of participants with at least 1 VOC that required admission to a healthcare facility and treatment with parenteral pain medication within 90 days from 35% for placebo to 23.8% for inclacumab).

As of June 2023, the Sponsor has decided to discontinue the study prior to full enrollment, with approximately 26% of the total number of planned participants randomized. The ultimate study sample size is based on screening and enrollment at the time of the decision to discontinue, rather than any statistical considerations.

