5.3. Efficacy Analyses

Efficacy analyses will be based on the ITT patient population (Section 4.1), with participants grouped according to the treatment assigned at randomization. Data from all randomized participants, regardless of treatment with study drug or adherence to the protocol will be included in the efficacy analyses.

Covariate Adjustment

Unless otherwise noted, analyses of primary and secondary efficacy endpoints will be adjusted for the following randomization stratification variables:

- Baseline HU use (yes; no)
- Number of VOCs in the 12 months prior to study entry (2 to 4 episodes; 5 to 10 episodes)

If convergence or model issues arise, then analyses will be simplified by excluding one of the above stratification variables.

Note: The additional randomization stratification variable of geographic region (North America; rest of world) will not be included in the analyses due to the early study discontinuation and the low number of subjects enrolled from North America.

For stratification variables, the value recorded in the clinical database (i.e., per case report form) will be compared to value captured in the IRT. If differences are observed, the values from the clinical database will be used in the analysis.

Statistical Tests

No adjustment for multiple comparisons will be performed.

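### The VOC-rate model could use the recorded prior-year VOC count instead of two classes, for a small gain in precision at almost no cost

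*SAP*

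**What the plan says.** SAP 5.3.2.3 compares the number of VOCs over 90 days by negative binomial regression, with log time at risk as offset, and says: "The regression model will include covariates for treatment group (inclacumab, placebo) and the randomization stratification factors". The Covariate Adjustment part of SAP 5.3 names two factors. One is baseline hydroxyurea use. The other is "Number of VOCs in the 12 months prior to study entry (2 to 4 episodes; 5 to 10 episodes".

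The number behind the two classes is available. Protocol 3.3.1.1, criterion 5, requires 2 to 10 prior VOCs from documented medical history and says that the index VOC does not count. SAP 5.2 lists "number of VOCs in the 12 months prior to the screening visit" among the baseline characteristics.

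The definitions of the prior and the on-study event are close. Criterion 5 needs a healthcare visit or remote contact, and adds: "Requires parenteral narcotic agents, parenteral nonsteroidal anti-inflammatory drugs (NSAIDs), or an increase in treatment with oral narcotics". The endpoint in SAP 2.2.2 likewise needs a healthcare visit or remote contact together with parenteral pain medication or increased oral narcotics.

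**The concern.** The prior-year count is close to a baseline measurement of the outcome. Cutting it at 4/5 treats 5 and 10 prior VOCs as equal and separates 4 from 5. Stratified randomization balances the two classes, not the counts within them. A log(count) term uses the same single degree of freedom and needs no new data.

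At stake is the precision of the rate ratio. Enrolment has stopped, so better use of data already collected is one of the few ways left to improve it.

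**Working it through.** **1. The plan's own figures.** SAP 2.3 gives a "planned sample size of up to 280 participants (140 participants per treatment group" and says that the trial stopped "with approximately 26% of the total number of planned participants randomized": 0.26 × 280 = 72.8, about 73 in all or 36 to 37 per arm.

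The stated design, which "was to provide approximately 90% power" for the primary endpoint, reproduces. For 35% against 17.5%, two-sided 0.05 and 90% power, a fixed design needs 131 per arm; 131/0.95 = 138, against 140 planned. With two looks at 75/140 = 0.536 information, Lan-DeMets O'Brien-Fleming spending and 0.95 × 140 = 133 evaluable per arm, power is 89.9% (pooled variance) or 91.0% (unpooled). The documents state no power, standard error or expected rate for the VOC-rate model, so there is no figure of theirs to reproduce for it.

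**2. Assumptions for the rate model (not in the documents).** Prior counts follow a gamma-Poisson model (mean 4 per year, shape 1 or 2) truncated to 2 to 10, with 43% to 44% having 5 or more. The placebo mean is 1.1 to 2.3 events per 90 days and the rate ratio 0.5 or 0.75. Extra frailty variance is 0 or 0.5. Hydroxyurea use is 50% with no effect. There were 600 runs per scenario at N = 73, with treatment, hydroxyurea use, the prior-VOC term and the log-time offset in the model.

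**3. Results.** With r the ratio of model standard errors, log(count) over two classes, the equivalent gain in sample size is 1/r² − 1. The last digit can differ because r is rounded here.

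| Scenario | SE, two classes | SE, log(count) | r | Gain in N | Empirical SD ratio |
|---|---|---|---|---|---|
| Shape 2, placebo mean 2.15, rate ratio 0.5, no extra frailty | 0.220 | 0.216 | 0.983 | 3.4% | 0.970 |
| Shape 2, placebo mean 2.11, rate ratio 0.5, extra frailty 0.5 | 0.281 | 0.278 | 0.989 | 2.2% | 1.003 |
| Shape 1, placebo mean 1.09, rate ratio 0.75, no extra frailty | 0.266 | 0.263 | 0.989 | 2.3% | 0.991 |
| Rate exactly proportional to recorded count, placebo mean 1.13, rate ratio 0.5 | 0.283 | 0.279 | 0.987 | 2.7% | 0.967 |
| As above, placebo mean 2.26 | 0.203 | 0.199 | 0.982 | 3.8% | 0.933 |

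Over all ten scenarios the gain in N was 1.6% to 6.4%: 0.016 × 73 = 1.2 to 0.064 × 73 = 4.7 participants. Power changed by about −1 to +3 points, for example from 72.3% to 71.7% and from 88.2% to 90.8%. The most favourable empirical SD ratio, 0.933, is worth 1/0.933² − 1 = 15% in N. It needs a rate exactly proportional to the recorded count and about 2.3 placebo events in 90 days.

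**4. Other assumed distributions.** A second set, with 1,200 replicates per scenario, gave variance ratios of 0.954 to 1.000; at best 1/0.954 − 1 = 4.8%, or 0.048 × 73 = 3.5 participants. Further sets gave 0.965 to 0.989 and 0.95 to 0.99.

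**5. Why the gain is small.** A 90-day count is mostly random variation, and two classes already carry much of the information. In the first row of the table, a model without any prior-VOC term has SE 0.229. The two classes remove 0.009 of the 0.013 that log(count) removes.

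**The case against.** The strongest reply is that nothing here is wrong. Adjusting for the factors used in randomization is valid, follows the design, and agrees with Protocol 8.4.3.2. The gain is a few participants at most, under rates that the documents do not supply. The endpoint is last in the testing order of Protocol 8.4.3.5, and the SAP introduction says that many analyses are limited or descriptive after the early stop. All of this stands, and it limits the point to an efficiency suggestion.

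It is also fair that the match between events is close but not complete. Prior VOCs come from medical history, while on-study VOCs are adjudicated (SAP 2.2.1). Participants' weekly recording targets episodes needing parenteral medication (Protocol 5.4.5), while the prior count includes episodes treated with increased oral narcotics. Error in the historical count weakens log(count). It does not remove the case for using the count, because the two classes are derived from the same history.

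A reader might infer that region belongs in the model too. SAP 5.3 says that "geographic region (North America; rest of world) will not be included in the analyses", and gives early discontinuation and few North American participants as the reason. With share f and rate ratio R, region explains a log-rate variance of f(1 − f)(ln R)². At an assumed f = 0.05 and R = 1.5 this is 0.0475 × 0.164 = 0.008; at f = 0.10 and R = 2 it is 0.09 × 0.480 = 0.043. In simulation with 10% North American participants, adding region changed the variance by +1% to −6%. The 6% gain needed a threefold region effect, which nothing in the documents supports.

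**Conclusion.** The point holds as a cheap improvement of low severity. The planned rate model is valid, and using the recorded count would make it slightly more precise. At about 73 participants the variance of the log rate ratio would be about 0% to 5% lower in one set of runs. In another its standard error would be about 1% to 3% lower, which is about 2% to 6% in variance. That is roughly 1 to 5 participants and does not change what a trial of this size can show. The figures rest on the assumed rates, dispersion and distribution of counts; the direction is consistent, and the lower end is no gain.

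Three further inferences are not supported:

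- **Changing the Cox model as well.** No gain was computed for it. At the planning rates about 36.5 × 0.35 + 36.5 × 0.175 = 19 first events would be expected, which is thin support for a richer model.
- **Reading the study-entry wording in SAP 5.3 as taking in the index VOC.** That section names the variable as a randomization stratification factor, and criterion 5 already excludes the index VOC.
- **Treating counts outside 2 to 10 as a defect of the model.** Such counts would be eligibility deviations, and a missing rule for them is a matter of detail.

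**What to change.** In SAP 5.3.2.3 only, and before unblinding, replace the two-class prior-VOC factor by log(number of VOCs in the 12 months before Screening, index VOC excluded). Keep baseline hydroxyurea use and the log-time offset. Keep the exact CMH and log-rank tests stratified as planned, and leave region and the Cox model as they are.

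The cost is a sentence or two of SAP text and no new data or degrees of freedom. Two downsides should be accepted openly: the model then assumes that the log rate is linear in log(count), and its covariate form differs from that of the stratified tests. If the change cannot be settled before unblinding, report it as a post hoc sensitivity analysis beside the planned model.
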